Study efficacy will be determined by comparing the rates of hospitalizations and ER visits between intervention and control study site veteran organ transplant recipients, while adjusting for baseline patient, provider and facility characteristics. Secondary measures include comparing estimated healthcare costs and determining dashboard functionality, dashboard actionability and pharmacist intervention types and acceptance rates. We will also assess the overall incidence and severity of drug-related problems and graft and patient survival rates and compare these between the intervention and control sites.

Interventions and Duration

The study will randomize 10 sites to usual care or usual care plus intervention in a parallel arm design and study duration will be 24-months.

The intervention will include a pharmacist that utilized a dashboard system to identify veteran organ transplant recipients with the potential of immunosuppressant medication-safety issues. The technology component of this intervention consists of the use of a dashboard system that performs population-level surveillance of organ transplant recipients and identifies those with potential drug-related problems, including non-adherence to immunosuppression medications, drug interactions, missing and worrisome trends in labs and recent hospitalizations and ED visits; then providing a real-time alert to the pharmacist, who will determine its relevance and intervene in an appropriate protocol-guided manner.

Sample Size and Population

There will be 10 sites included in this study with an estimated average of 169 veterans per site, totaling 1,689 veterans across the entire study population, divided approximately equally between the intervention and usual care groups

The patient population will consist of veterans that received solid organ transplants (kidney, liver, pancreas, heart, or lung) and receive their immunosuppression medications through the VA system. Patients will be identified using ICD-9 or 10 codes and VA medication prescription information.

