4 SELECTION AND ENROLLMENT OF STUDY SITES AND PATIENTS

Patients will be included in this study if they are veteran organ transplant recipients that receive immunosuppressant medications through the VA system. Organ transplant recipients will be identified using ICD-9/10 codes from the VA electronic health record (CPRS), with this data housed in the CDW. Once identified, active medications will be queried and those receiving immunosuppressant medications to prevent rejection (tacrolimus, cyclosporine, azathioprine, mycophenolate, sirolimus, everolimus, or belatacept) will be included in the study. There are no exclusion criteria for patients in this study as recruitment is at the VA site-level. As this is a cluster-randomized study and randomization will occur at the site level and not the patient-level, participants will not be recruited for the study, and data collection will occur through querying and linking the VA CDW, the SRTR transplant registry and CMS data repositories. We will request waiver of written documentation of patient informed consent. We will also request HIPAA authorization waiver as well for all patients. The following protected health information (PHI) elements will be required to complete the study with the HIPAA authorization waiver.

| PHI Required for Study | Rationale |
|--|---|
| Social Security Number | Require real SSNs to create finder file and send to Scientific Registry of Transplant Recipients (SRTR) to acquire baseline transplant information and graft outcomes |
| Date of transplant, date of clinical events (including graft loss, rejections, | Require dates to ensure events occurred during the study period and to conduct |

| | |
|--|--|
| hospitalizations, emergency department visits and death) | time to event survival analyses for primary and secondary aims |
| Zip codes | Require zip code to assess and adjust for potential geographic confounding in multivariable analyses |

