9.3.1 Primary outcome

The primary outcome for this study will include the overall rate of ER visits and hospitalizations, compared between the intervention and control groups. These encounters will be captured electronically throughout the 24-month study through the use of the CDW, stored in the VINCI environment. In addition, to ensure encounters are captured in a comprehensive manner, we will also link the VA CDW data to CMS (Medicare) claims data and capture non-VA ER and hospitalization encounters (after study completion). As most transplant patients are dual users and have Medicare

insurance benefits, this linkage will provide a more accurate assessment of these health care utilization.³ We expect ER visits and hospitalizations to significantly decrease within the intervention arm, towards the latter half (second 12-months) of the study due to a lag effect of the intervention on this outcome. This expectation is based on our previous research in this field and assessment of pharmacist interventions on medication safety and reduced adverse drug events requiring hospitalization. ER visits and hospitalizations will be assessed and compared as described in the statistical analysis plan. These will be defined based on encounter criteria within the CDW and CMS data: all-cause ER visits and all-cause hospitalizations leading to at least one overnight stay will be included as events.

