9.3.2 Secondary outcomes

Secondary assessment will include a cost benefit analysis. Overall health care costs accrued during the 24-month study, as well as those accrued in the 24-months prior to study initiation will be analyzed and compared between the control and intervention groups. Cost data will be standardized using the VA Health Economics Resource Center (HERC) definitions, which normalizes regional differences in costs due to variation in cost of living indices. As with the primary outcome, we will also acquire and link CMS claims data to gain a comprehensive assessment of costs, including those that accrue from non-VA care (after study completion). Costs will also be sub-analyzed into three predominant categories: inpatient costs, outpatient costs and pharmacy costs, as described in the statistical analysis plan. To fully assess if the intervention is has a direct monetary benefit, we will measure costs of the intervention will include estimates of time and resources to implement the dashboard and train and support the intervention site pharmacists. Similar to primary outcome, we expect that as ER visits and hospitalizations decrease within the intervention arm, there will be a corresponding decrease in overall costs as well, predominantly driven by inpatient costs. We expect this decrease to occur during the second 12 months of the study period, as the intervention is likely to have a lag effect on this outcome as well.

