9.4 Data Analyses

The data analysis will incorporate the intent-to-treat principle; namely, all participants enrolled in the intervention group will be included in the analysis and compared to all of the patients captured within the control group. If a patient dies, has graft loss or moves out of their study site, their data will be censored at that time point. For comparative statistical assessments within the utilization outcomes, the two groups will be compared using a generalized linear mixed models (GLMM) approach.⁵⁴ This approach allows for measurement of participants at different time points, clustering by study site, missing data under the assumption of missing at random (MAR), time varying or invariant covariates, and can also account for the effect of correlated longitudinal measurements within participants. In addition, GLMM accommodates a wide range of distributional assumptions such as dichotomous (e.g. binomial), count (e.g. Poisson), continuous

(e.g. Gaussian), and categorical or ordinal outcomes. For comparing the primary outcome (ED visit and hospitalization rates), we will use GLMM (with appropriate link function) with counts of these events as the outcome variable and intervention group (yes/no) as the primary independent variable. This analysis is equivalent to Poisson regression or negative binomial regression (in the case of over-dispersion), both special cases of GLMM. Additional adjustment covariables will be added to the model in a second set of analyses. Covariates will include patient sociodemographics: age, sex, race, comorbidities (using modified Elixhauser definitions), marital status and education. In these models, donor information (age, sex, race, deceased or living) and transplant characteristics (HLA mismatches, ischemic times, panel reactive antibody levels, time since transplant) will also be included. This will assist in making valid intervention effect estimates after accounting for baseline differences, as there may be patient-level differences between groups. The magnitude of between intervention differences on outcome variables (effect sizes) at each time point will be estimated using appropriate contrasts in the corresponding GLMM models.

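### The plan does not say whether the unadjusted or the adjusted model decides the primary outcome, and the cost model's listed covariates omit the two prior years of cost that the trial obtains

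*Combined protocol and SAP*

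**What the plan says.** **Primary outcome.** The synopsis, under Design and Outcomes, ties the determination of efficacy to a comparison of encounter rates "while adjusting for baseline patient, provider and facility characteristics". Section 9.4 describes the primary model as a generalized linear mixed model "with counts of these events as the outcome variable and intervention group (yes/no) as the primary independent variable". It then says: "Additional adjustment covariables will be added to the model in a second set of analyses". The variables named there are patient (age, sex, race, comorbidities, marital status, education), donor (age, sex, race, deceased or living) and transplant (HLA mismatches, ischemic times, panel reactive antibodies, time since transplant). None describes a provider or a facility. Of the adjusted analysis, section 9.4 says: "This will assist in making valid intervention effect estimates after accounting for baseline differences". Section 9.3.1 defines the target: "The primary outcome for this study will include the overall rate of ER visits and hospitalizations". Section 9.2 bases power on a Poisson comparison that allows for intra-cluster correlation only.

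**Cost.** Section 9.3.2 says that costs in the study period and "those accrued in the 24-months prior to study initiation will be analyzed and compared" between groups. Section 9.4 obtains cost for two years before and two years during the study. It adjusts the cost models for the same sociodemographic, donor and transplant variables, and pre-study cost is not on that list. Section 9.4 also names propensity score calibration, without saying what goes into it.

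**The concern.** The synopsis and section 9.4 describe different primary comparisons with different covariate sets, and no section names the one that decides the trial. With five sites per arm, chance imbalance between arms is likely, and section 9.4 itself expects that patients may differ between groups. The two analyses can then give different answers. If the deciding model is not fixed in advance, it can be picked once both p-values are known, and the error rate of that choice exceeds that of either test.

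The cost gap is of a different kind. A baseline measure of the outcome is already being collected, but the model has no written place for it. Its use is left to a later decision, and it may go unused.

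**Working it through.** **1. The plan's own figure.** Inputs from section 9.2: 1.269 events per person-year, rate ratio 0.75, intra-cluster correlation 0.05, 10 sites, 80% power, two-sided 0.05, with 24 months of follow-up.

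- Events per patient: control 1.269 × 2 = 2.538; intervention 0.75 × 2.538 = 1.9035.
- Patients per arm before clustering: (1.960 + 0.842)² × (1/2.538 + 1/1.9035) / ln(0.75)² = 7.849 × 0.9194 / 0.08276 = 87.2.
- Design effect at 1,350/10 = 135 per site: 1 + 134 × 0.05 = 7.70.
- Total: 2 × 87.2 × 7.70 = 1,343, against the stated 1,350. Then 1,350/0.85 = 1,589, against the stated 1,600.

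The sample size reproduces, and it does so with no covariate in the model.

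**2. Side by side.**

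| | Synopsis | Section 9.4 |
|---|---|---|
| Adjusted? | Yes, as part of judging efficacy | Arm first, covariates in a second set |
| Patient variables | Yes | Yes, second set |
| Provider, facility | Yes | None listed |
| Donor, transplant | Not named | Yes, second set |
| Called the deciding analysis? | No | No |

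The AIC/BIC rule in section 9.4 is described for choosing among Poisson, negative binomial and zero-inflated forms. It does not settle adjusted against unadjusted.

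**3. What an open choice costs.** Site-level simulation, 400,000 trials per setting.

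- Patients per site: 1,689 × 0.85 / 10 = 143.6.
- Between-site variance of the log rate (assumed mapping from the intra-cluster correlation): (0.05/0.95)/2.538 = 0.0207.
- Sampling variance of a site log rate: 1/(143.6 × 2.538) = 0.0027 in control; 0.0027/0.75 = 0.0037 in intervention at rate ratio 0.75.
- Site log rate = arm + X + U + error. X is the part carried by the section 9.4 covariates, a share R² of 0.0207, and U is the rest.
- Unadjusted test: t on 10 site log rates, 8 df. Adjusted test: the same after removing X, still 8 df because the coefficients come mainly from within-site data.

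| R² (assumed) | Either test alone, no effect | Either significant, no effect | False claim of benefit (2.5% nominal) | Verdicts differ, no effect | Verdicts differ, rate ratio 0.75 |
|---|---|---|---|---|---|
| 0 | 5.0% | 5.0% | 2.5% | 0% | 0% |
| 10% | 5.0% | 6.5% | 3.3% | 3.1% | 8.9% |
| 25% | 5.0% | 7.4% | 3.7% | 4.9% | 14.8% |
| 50% | 5.0% | 8.4% | 4.2% | 6.7% | 21.9% |

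Repeat runs agree to about 0.1 point. As a cross-check, two normal test statistics with correlation 0.95 to 0.5 give 6.5% to 9.1%.

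**4. Cost.** The period obtained (two years before, two during) and the adjustment list were compared item by item. Pre-study cost appears in the first and not in the second. No figure is computed, because the documents give no correlation between prior and on-study cost.

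**The case against.** Section 9.4 is the operative analysis section. It introduces the arm-only model as the one for the primary outcome and puts covariates afterwards. Section 9.2 powers the trial without covariates. The synopsis sentence is one line, and the plan runs both analyses. On this view the unadjusted model is primary, and only a label is missing. Much of this stands: it is the more natural reading. But the label is absent, the synopsis attaches efficacy to the adjusted comparison, and section 9.4 presents adjustment as an aid to valid estimates.

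The size is also open to challenge. The 5.0% baseline comes from the t reference with 8 df. With a normal reference each test alone gives about 8.6%, and no section names a small-sample method. At R² of 2% or 5% the inflated rate is only about 5.7% or 6.2%. Most of the disagreement at rate ratio 0.75 is power gained by adjustment (about 12 of 15 points at R² = 25%, 21 of 22 at 50%), so it is not a count of errors. These objections stand.

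Some stronger readings are tempting but not supported:

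- A reader might infer a further conflict from the zip-code entry in section 4 ("Require zip code to assess and adjust for potential geographic confounding in multivariable analyses"). That is a justification for holding identifiers. It promises no term in the primary model, and the section 9.4 list is worded openly.
- A reader might infer that effects "at each time point will be estimated using appropriate contrasts in the corresponding GLMM models" compete with the overall rate in section 9.3.1. They are effect-size estimates and do not displace it.
- A reader might infer that prior cost has no use. Section 9.3.2 gives it one, a comparison between groups. A pre/post repeated-outcome model is a natural reading, though it is not written.

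**Conclusion.** The point holds as a gap in specification. The synopsis and section 9.4 differ on whether the primary comparison is adjusted and for what. The unadjusted model is the likelier primary, but no section says so. If either result could be claimed, two-sided type I error would be about 6.5% to 8.4%, and a false claim of benefit 3.3% to 4.2% against 2.5%. This is the extreme case in which whichever result is significant gets reported. It rests on two assumptions that the documents do not supply: covariates explaining 10% to 50% of between-site variance, and a t reference with 8 df. The mapping of the intra-cluster correlation to the log-rate scale is also assumed. If the covariates explain no between-site variance, there is no inflation.

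Confidence is high on the wording gap and lower on its size. A reader might infer that the sample size is wrong or that one of the two models is invalid; neither follows. The cost item is an available improvement, not an error in a stated figure.

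**What to change.** **1. Primary outcome.** Before outcome data are seen, name one deciding model with a fixed covariate list, and state that the deciding contrast is the overall 24-month rate ratio, in line with section 9.3.1. Align the synopsis with section 9.4, including whether provider and facility variables are in. Label the other model a sensitivity analysis. Either choice is defensible if it is made in advance. The cost is protocol and SAP wording.

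**2. Cost models.** Include pre-study cost, either as a baseline covariate or as the pre-period value of a repeated outcome, but not both. Add a rule for patients with less than 24 months of look-back, because section 4.2 allows rolling entry. The cost is one modelling rule; the data are already planned under sections 9.3.2 and 9.4.

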4.2 Exclusion Criteria

- There are no exclusion criteria for patients in this study as recruitment is at the level of the VA site.
- All veterans meeting inclusion criteria will be monitored by the dashboard system and will be included in the outcomes assessment. Patients may enter or exit the study in a rolling manner, which will be accounted for during analyses.

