9.2 Sample Size and Randomization

Based on the projected enrollment numbers, there is ample power to detect a statistically significant difference between the intervention and control groups with regards to the primary aim of hospitalization and ED visit rates. To determine this, we used data from a recent national study conducted between 2009-2012.⁵³ These results demonstrated that the rate of ED visits after transplant was 1.269 per person-year and 48% of those ED visits resulted in hospitalization. We will enroll 10 sites (5 sites for each study arm) and will have a total of just more than 1,600 patients that are roughly split between the intervention and control sites. We used a conservative estimate of an intra-cluster correlation of 0.05 and calculated a sample size of 1,350 to allow us to detect a 25% relative decrease in ED visit and hospitalization rates with 80% power. The 25% relative improvement in rates is a conservative estimate of intervention effect, based on previous pharmacist-led initiatives the investigators have conducted.^{15,16} After allowing for 15% loss to follow up, we require a total of 1,600 to meet study power. We expect to have 1,689 patients based on site estimates. These power calculations were conducted using a two-sided test for counts with Poisson regression adjusting for intra-cluster correlation and with alpha set at 0.05.

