9.2.1 Treatment Assignment Procedures

Randomization will occur at the site level (cluster randomized trial). Ten sites will be randomized to either the intervention arm or usual care arm using statistical software (SAS, SAS Institute, Cary, NC). Randomized will occur after all sites have agreed to participate and site-level regulatory approval has occurred. Randomization will be stratified by site using estimated sample size (<125 vs. ≥ 125 veteran organ transplant recipients). This will be done to ensure an approximate even distribution of patients across study arms.

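### Organ type is neither a randomisation stratum nor a named covariate, so a chance difference in organ mix between the two sets of five sites is at best partly adjusted for

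*Combined protocol and SAP*

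**What the plan says.** The synopsis (Sample Size and Population) defines the population as "veterans that received solid organ transplants (kidney, liver, pancreas, heart, or lung"). Section 4.1 selects patients by transplant diagnosis codes plus a VA-dispensed anti-rejection drug. Section 4.2 adds no restriction: "There are no exclusion criteria for patients in this study as recruitment is at the level of the VA site".

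Ten sites are allocated five to each arm (Section 9.2). Section 9.2.1 states that "Randomization will be stratified by site using estimated sample size", with a cut at 125 recipients. Section 4.3 describes the same single stratum.

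Section 9.4 first compares encounter counts with intervention group as the primary independent variable and clustering by site. Then "Additional adjustment covariables will be added to the model in a second set of analyses". The patient covariates are "age, sex, race, comorbidities (using modified Elixhauser definitions), marital status and education". The donor covariates are age, sex, race and living or deceased status. For the transplant itself, "transplant characteristics (HLA mismatches, ischemic times, panel reactive antibody levels, time since transplant) will also be included". Organ type is not on any of these lists. The cost models in the same section refer back to the same covariates. No analysis by organ is described.

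Two other statements bear on the point. The synopsis (Design and Outcomes) says the efficacy comparison will adjust for baseline features of patients, providers and facilities. Section 10.1 says the SRTR linkage will supply the baseline donor, recipient and transplant data.

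**The concern.** Which organ a patient received is among the most basic baseline facts about a transplant population. Here it enters neither the allocation nor the specified adjustment. With five sites per arm, randomisation cannot be relied on to even out a characteristic whose mix may differ from site to site. A random site effect does not help: it allows for variation between sites in the standard error, but it does not take an organ-mix difference between arms out of the point estimate.

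Section 9.4 gives accounting for baseline differences as the purpose of the second set of models. If encounter rates or costs differ by organ, those models as listed would leave part of one obvious baseline difference in the estimate. Readers would have no prespecified analysis to show whether it mattered. Adding organ type after outcomes are known would look like a post hoc choice in a trial of only 10 clusters.

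**Working it through.** **1. The plan's own sample size, to see whether the point touches it.** Inputs from Section 9.2: 1.269 ED visits per person-year, rate ratio 0.75, two-sided alpha 0.05, power 80%, ICC 0.05. Assumed here: 24 months of follow-up for every patient and 1,350/10 = 135 per site.

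- Intervention rate: 0.75 × 1.269 = 0.95175.
- Person-years per arm before clustering: (1.960 + 0.842)² × (1/1.269 + 1/0.95175) / (ln 0.75)² = 174.4, which is 87.2 patients over two years.
- Design effect: 1 + 134 × 0.05 = 7.7.
- Total: 2 × 87.2 × 7.7 ≈ 1,343, against 1,350 stated.
- With 15% loss: 1,350/0.85 ≈ 1,589, against 1,600 stated.

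The planned numbers reproduce, and adding a covariate changes none of them.

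**2. Size of a possible shift.** The documents give no organ shares and no organ-specific rates. The one encounter rate they use comes from a study whose title concerns kidney recipients. All inputs in this step are therefore assumptions. Let a and b be the kidney shares in the control and intervention arms, and h the non-kidney to kidney rate ratio. With no intervention effect, the apparent rate ratio is

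RR = (b + (1 − b)h) / (a + (1 − a)h).

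| a | b | h | RR |
|---|---|---|---|
| 0.60 | 0.75 | 1.5 | 1.125/1.200 = 0.938 |
| 0.60 | 0.75 | 2.0 | 1.250/1.400 = 0.893 |
| 0.55 | 0.80 | 1.5 | 1.100/1.225 = 0.898 |
| 0.55 | 0.80 | 2.0 | 1.200/1.450 = 0.828 |

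On the log scale, the first two rows are 22% and 39% of the planned effect: ln 0.938/ln 0.75 and ln 0.893/ln 0.75. With the arms swapped, a true rate ratio of 0.75 would appear as 0.75/0.938 = 0.80 or 0.75/0.893 = 0.84. If non-kidney rates are lower than kidney rates, the direction also reverses.

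**3. How probable such gaps are.** Let s be the between-site SD of the kidney share (assumed). For simple 5 versus 5 allocation of equal-sized sites, the arm difference has SD s × √(2/5). Two-sided normal probabilities:

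| s (points) | SD of arm gap | P(gap ≥ 10) | P(gap ≥ 15) | P(gap ≥ 25) |
|---|---|---|---|---|
| 5 | 3.2 | 0.2% | about 0% | about 0% |
| 10 | 6.3 | 11% | 1.8% | 0.01% |
| 15 | 9.5 | 29% | 11% | 0.8% |
| 20 | 12.6 | 43% | 24% | 4.8% |

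The 15-point gap is plausible if sites differ a good deal. The 25-point gap behind 0.898 and 0.828 is a tail case even at s = 20.

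**4. Relation to the planned uncertainty.** The planning standard error of the log rate ratio is |ln 0.75|/2.80 = 0.103. With s = 15 points and a mean kidney share of 67.5%, organ mix contributes 0.095 × (h − 1)/(1 + 0.325(h − 1)). That is 0.041 for h = 1.5 and 0.072 for h = 2, or about 16% and 49% of the planning variance. This variation falls within the between-site variance that the ICC is meant to cover. It is not additional to it.

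**The case against.** The strongest reply is that sites are randomised. Any organ-mix difference is then chance imbalance, already carried in the ICC and the site clustering, and valid cluster-level inference remains valid without adjustment. That stands. A reader might infer that the effect estimate is biased or that imbalance is likely. The documents support neither: they give no organ mix, by site or overall. What remains is that in this single allocation of 10 sites the point estimate can be shifted, and a known cause of such a shift could be adjusted for at almost no cost.

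Second, the list in Section 9.4 may not be exhaustive. Section 4 says zip codes are needed for geographic adjustment, and the synopsis promises provider and facility adjustment, yet none of these is on the list. So organ type is best described as not named, rather than ruled out. Living or deceased donor, ischemic time and comorbidities may also act as partial proxies.

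Three further inferences are tempting and should not be drawn:

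- That the plan would impute HLA or antibody data for non-kidney recipients. Section 9.4 adopts missing-at-random methods only after examining missingness and if there is no reason to think otherwise. The documents nowhere say that these variables are lacking for other organs.
- That Section 2.1 shows organ-specific encounter rates. It describes what follows graft loss, not ED visits or admissions, and patients are censored at graft loss.
- That adding the covariate repairs the unadjusted comparison. It does not, which is why a tabulation is also needed.

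**Conclusion.** The point holds as a gap in the specified adjustment. Five organ types are pooled, the only stratum is site size, and organ type is absent from the covariates named for the utilization and cost models. A chance difference in organ mix is left alone in the unadjusted model and is at best partly removed in the adjusted ones.

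Its size cannot be determined from the documents. As an illustration, a 15-point difference in kidney share with a non-kidney rate 1.5 to 2 times the kidney rate gives a null rate ratio of about 0.94 to 0.89, in either direction. This rests on assumed shares and rates, and on no proxy adjustment. The chance of a gap that large runs from negligible to about 24% as the assumed site SD goes from 5 to 20 points. The planned sample size is unaffected.

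**What to change.** In Section 9.4, name organ type as a prespecified patient-level covariate in the adjusted utilization and cost models. Take it from the inclusion diagnosis codes and the SRTR linkage. Fix the categories, including how multi-organ recipients and small groups are handled, before outcomes are examined. Report a table of organ type by arm and by site, so that the unadjusted result can be read against the observed mix.

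The cost is a few lines of plan text and a few model parameters (four if the five organs are kept separate). As a patient-level covariate it uses no cluster-level degrees of freedom, and it should need no data beyond the codes and linkage already planned.
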